**Table 5: Potentially Clinically Significant Values for Specific Laboratory Parameters**

Laboratory Parameter	Units	Criteria for PCS Values (Observed values)	
		High	Low
Hemoglobin -male	g/L	>185	<115
Hemoglobin -female	g/L	>170	<100
Hematocrit-male	Fraction of 1	>0.55	<0.385
Hematocrit-female	Fraction of 1	>0.49	<0.345
Platelet count	10  /L	>600	<125
Leukocytes	10  /L	>15	<2.5
Basophils	10  /L	>0.5	NA
Eosinophils	10  /L	>1.5	NA
Neutrophils	10  /L	NA	<1.5
Lymphocytes	10  /L	>6.0	<0.5
Monocytes	10  /L	>1.4	NA
Albumin	g/L	>70	<28
Blood urea nitrogen	mmol/L	>10.71	NA
Calcium	mmol/L	>2.75	<2.0
Chloride	mmol/L	>120	<90
Creatinine	mmol/L	>3xULN or >3x Baseline	
Gamma Glutamyl Transferase	U/L	>3xULN	
Glucose	mmol/L	>13.9	<2.8
Sodium	mmol/L	>150	<132
Potassium	mmol/L	>5.4	<3.3
Protein	g/L		<45
Bicarbonate	mmol/L	>34	<18
Phosphorus	mmol/L	>1.94	<0.61
Liver Function Tests (LFT)			

Laboratory Parameter	Units	Criteria for PCS Values (Observed values)		
		High	Low	
Bilirubin	µmol/L	>2xULN		NA
Aspartate Aminotransferase	U/L	>3xULN		NA
Alanine Aminotransferase	U/L	>3xULN		NA
Alkaline Phosphatase	U/L	>3xULN		NA
Coagulation				
International Normalized Ratio (INR)	NA	>1.5x ULN		NA
Partial thromboplastin time (PTT)	sec	>1.5x ULN		NA

#### 8.4.4. Vital Signs

Vital signs include systolic and diastolic blood pressure, heart rate, temperature, and respiratory rate (if not on mechanical ventilation). Systolic and diastolic blood pressure and heart rate are to be collected supine or prone. Respiratory rate and temperature are collected once in any position. Descriptive summaries of observed values and changes from baseline will be provided for vital sign parameters - by windowed visit and treatment group.

Additionally, the number and percentage of participants with PCS and PCS values will be summarized. PCS values will be identified for vital sign parameters as outlined in [Table 6](#).

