### 8.1. Participant Inclusion Criteria

Each eligible participant must:

1. Be confirmed positive for SARS-CoV-2 infection as determined by polymerase chain reaction at screening or within 2 weeks prior to screening
2. Be aged 18 years or older
3. Be able to provide written informed consent, signed by participant or by proxy (legally acceptable representative)
4. Have a presumptive diagnosis of ARDS at screening and  $\text{PaO}_2/\text{FiO}_2$  (PF ratio)  $<300$  within 48 hours prior to randomization
5. Be intubated and receiving mechanical ventilation prior to randomization. Note that participants must have initiated mechanical ventilation within 48 hours prior to written informed consent, or have an immediate clinical plan for such intervention at time of written informed consent
6. Be likely to survive, in the opinion of the investigator, for at least 72 hours from the time of written informed consent

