#### 12.1.3. Vital Signs

Vital signs include systolic and diastolic blood pressure, heart rate, temperature, and respiratory rate (if not on mechanical ventilation) and are to be recorded for the times specified in Figure 1. Systolic and diastolic blood pressure and heart rate are to be collected supine or prone. Respiratory rate and temperature are collected once in any position.

Additionally, respiratory rate, heart rate, and blood pressure should be recorded for any participant who experiences an AESI (defined in Section 12.2.3) as soon as is feasible after the onset of the event and recorded as unscheduled on the CRF.

[REDACTED]

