## 5. STUDY DESIGN

### 5.1. Overall Design

This is a randomized, double-blind, placebo-controlled study designed to evaluate treatment with brexanolone in approximately 100 participants with ARDS due to COVID-19. Participants and their family or caregivers, clinicians, site staff, and sponsor personnel will be masked to treatment allocation.

Participants with ARDS and SARS-CoV-2 infection who give informed consent (or for whom consent is given by a proxy) and who are currently intubated and receiving mechanical ventilation as part of standard of care or who are on an immediate clinical plan to receive such intervention will be eligible for screening. All participants must have mechanical ventilation in place prior to randomization. Eligible participants will be stratified by age (<70 or  $\geq$ 70 years) and randomized 1:1 within each stratum to receive either brexanolone plus standard of care or placebo plus standard of care.

Participants will receive continued standard of care in addition to a continuous intravenous (IV) infusion of investigational product (IP) – brexanolone or placebo for 60 hours. The infusion must be initiated within 6 hours from the time of randomization. The blinded 60-hour infusion will be administered at a dose of 70 mcg/kg/h for 58 hours followed by a 2-hour taper at 35 mcg/kg/h. Transfer out of the ICU is not an indication to discontinue the infusion of investigational product.

Brexanolone may potentiate the sedative effects of co-administered anesthetics. During IP infusion, if sedation levels are deeper than intended, the dose(s) of sedative anesthetics should be titrated to the desired effect rather than adjusting the dose of IP (see Section 7.4 of the study protocol for additional details).

Dose adjustment is permitted in the event that a participant is experiencing unplanned sedation/somnolence when no longer on any sedating agents or if the participant experiences an intolerable adverse event (AE) determined by the investigator to be related to IP. Details regarding dose adjustment criteria and procedures are provided in Section 7.4 of the study protocol.

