## 8. STATISTICAL ANALYSIS

### 8.1. General Considerations

Unless otherwise specified, continuous endpoints will be summarized with n, mean, standard deviation (SD), median, minimum (min) and maximum (max). The min and max will be reported with the same number of decimal places as the source (raw) data. Mean and median will be reported to 1 decimal place more than the source (raw) data and standard deviation will be reported to 2 decimal places more than the source (raw) data, but no more than 4 decimal places. Any values that require transformation to standard units (metric or SI) will be converted with the appropriate corresponding precision.

Categorical variables (eg, presence of an AE) will be summarized using counts and percentages. Percentages will be presented to 1 decimal place unless otherwise specified.

All participant data, including those derived, that support the tables and figures will be presented in the participant data listings. Some data may be presented only in participant data listing with an underlying table or figure; these will be indicated in relevant sections below.

All summaries will be provided by treatment – either by treatment assigned at randomization, or actual treatment received. Actual treatment is defined as:

- Brexanolone – if the participant was exposed to brexanolone;
- Placebo – if the participant received placebo and not a single dose of brexanolone.

For the purpose of all safety and efficacy analyses, baseline is defined as the last non-missing measurement on or prior to the initiation of IP, unless stated otherwise.

P-values will be reported to four decimal places, with p-values less than 0.0001 reported as “<0.0001”. P-values larger than 0.9999 will be reported as “>0.9999”.

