**Table 6: Potentially Clinically Significant Values for Vital Sign Parameters**

Vital Sign	Units	Criteria for PCS Values (Observed values)		Criteria for Change from Baseline values (PCSC)	
		High	Low	Increase	Decrease
Heart rate (supine and prone)	Beats/min	>120	<40	NA	NA
Systolic Blood Pressure (supine and prone)	mmHg	>180	<90	≥30	≥30
Diastolic Blood pressure (supine and prone)	mmHg	>110	<50	≥20	≥20

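### Planned change from baseline in respiratory rate will mostly be missing or compare pre-intubation with post-extubation values, and Table 6 sets no limits for respiratory rate

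*SAP*

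**What the plan says.** - **Collection.** Protocol 12.1.3 lists the vital signs with "respiratory rate (if not on mechanical ventilation) and are to be recorded for the times specified in Figure 1". SAP 8.4.4 repeats the condition. Protocol 12.1.3 separately asks for respiratory rate, heart rate and blood pressure soon after the onset of any adverse event of special interest (AESI), with no ventilation condition.
- **Entry.** Protocol 8.1, criterion 5, requires each participant to "Be intubated and receiving mechanical ventilation prior to randomization". SAP 5.1 agrees: "All participants must have mechanical ventilation in place prior to randomization". There are two routes in: "participants must have initiated mechanical ventilation within 48 hours prior to written informed consent, or have an immediate clinical plan for such intervention".
- **Baseline.** SAP 8.1: "baseline is defined as the last non-missing measurement on or prior to the initiation of IP". SAP 8.1.2 adds that visit windows do not apply to baseline. Neither section has a separate rule for respiratory rate.
- **Analysis.** SAP 8.4.4: "Descriptive summaries of observed values and changes from baseline will be provided for vital sign parameters", by windowed visit and arm. SAP Table 3 marks vital signs for raw value, change from baseline and PCS. Change from baseline in vital signs is a listed endpoint in Protocol 6.2.2 and SAP 4.2.
- **PCS limits.** Protocol 13.6.3 and SAP 8.4.4 plan PCS summaries for vital signs. SAP Table 6, "Potentially Clinically Significant Values for Vital Sign Parameters", has rows for heart rate, systolic pressure and diastolic pressure only.

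**The concern.** Each rule is reasonable alone, but for respiratory rate they do not fit together. The collection rule removes the parameter during the period in which a baseline would be taken, while the analysis rule still calls for a difference from that baseline.

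The parameter matters here because both documents treat excess sedation as a risk of this drug. Protocol 7.4 provides for participants who are off all sedating agents but still receiving infusion. Unplanned sedation/somnolence and reintubation are AESIs (Protocol 12.2.3). Respiratory rate off the ventilator is one of the few routine measurements bearing on this. Its change table would say little, and no limit-based count by arm is planned for it.

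**Working it through.** The plan states no figure for this point, so the check sets the rules side by side. The arithmetic is limited to timing and a row count.

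**1. When can a baseline respiratory rate exist?** Inputs are ventilation begun up to 48 h before consent, or planned at consent (Protocol 8.1); consent to randomization at most 48 h (Protocol 7.1); and randomization to infusion at most 6 h (Protocol 10.5, SAP 5.1).

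- *Already ventilated at consent.* Time on the ventilator at infusion start can reach 48 + 48 + 6 = 102 h. No scheduled respiratory rate is due in that period. A baseline would have to come from a reading before intubation. Protocol 8 admits standard-of-care results for screening, but only within the windows of Figure 1, which is not reproduced in the copy reviewed.
- *Consented before intubation.* A screening value can exist. It predates intubation, and time on the ventilator by infusion start can reach 48 + 6 = 54 h. The value is at least as old as that time.
- *Exceptions.* A participant who comes off the ventilator between randomization and infusion, a gap of at most 6 h, could have a true off-ventilator baseline. An AESI-triggered reading before infusion is also possible in principle. Both should be rare.

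**2. When can a change be computed?** It needs a baseline and a later value. Let f be the share with a pre-intubation reading that qualifies as baseline, and g the share of those who later have an off-ventilator reading in the window:

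share with a change = f × g, which cannot exceed f.

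If f is below one half, the change is missing for most participants whatever g is. If f is larger, the result depends on g. Death and continued ventilation lower g, as does discharge, since only telephone assessments continue after it (notes to Protocol Figure 1). The documents give neither f nor g.

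**3. What does a computed change measure?** The baseline is usually taken before intubation and the later value after extubation. The difference spans a change of respiratory state as well as exposure to study drug. The participants who supply it are those who came off the ventilator, an event after randomization that treatment is intended to influence.

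**4. PCS coverage.** Five vital signs are listed: systolic pressure, diastolic pressure, heart rate, temperature and respiratory rate. Table 6 has rows for three. 5 − 3 = 2 have no limits: respiratory rate and temperature.

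**The case against.** Much of what one would ask for is already in the plan. SAP 8.4.4 summarizes observed values by window and arm, and SAP 8.1 supplies n, minimum and maximum. SAP 8.1.2 windows vital signs by 12 hours to Hour 72 and then essentially by day from Day 5, and it admits unscheduled readings. A sparse change column would be visible from its n. The choice of which vital signs receive PCS limits belongs to the sponsor, and the PCS sections do not name the parameters. All of this stands. It reduces the point to one change-from-baseline summary and one gap in a table.

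A reader might infer three stronger statements that the documents do not support:

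- *Respiratory rate is never recorded on the ventilator.* AESI-triggered readings carry no ventilation condition. They add mainly post-baseline values, so they do not repair baseline.
- *No change can be computed for anyone already ventilated at screening.* No age limit on baseline is stated, and Figure 1 cannot be checked. A tight screening window would make an empty baseline more likely, whereas a loose one would admit a pre-intubation value.
- *Nothing captures low or high rates by arm.* Observed-value summaries do so in part. Clinically significant vital-sign changes become adverse events (Protocol 12.2.1) and are tabulated by arm. What is missing is a count against numeric limits.

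The selected subset also affects the observed-value table. That cannot be removed, but labelling the table off-ventilator and showing n makes it plain.

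**Conclusion.** The point holds as a minor one. The planned change from baseline in respiratory rate will be missing for most participants and otherwise will usually compare pre-intubation with post-extubation values in a subset selected after randomization. It is not interpretable as a drug-safety measure in either arm. Table 6 leaves respiratory rate and temperature without limits although vital-sign PCS summaries are planned.

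Missing for most is an inference. It assumes either that fewer than half of participants have a qualifying pre-intubation reading or that enough of those who do never have a later off-ventilator reading. The trial stopped early (SAP 6.1), so counts are likely to fall below those expected from the planned 100.

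A reader might also infer a spurious fall of a definite number of breaths per minute, or a false drug effect. The documents give no respiratory rates before intubation or after extubation and no split between the two entry routes, so no size can be derived. That a pre-intubation rate reflects distress is a clinical inference. Any shift due to the baseline rule would be expected in both arms, so it would not alone create a difference between them.

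The effect is limited to descriptive safety tables. The primary and key secondary analyses do not use respiratory rate.

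**What to change.** 1. In SAP 8.4.4, with a footnote to Table 3, drop change from baseline for respiratory rate. Keep the planned observed-value summary by window and arm, labelled as off-ventilator with n. Record this in SAP 6.1, because it departs from Protocol 6.2.2 and 13.6.3.
2. Add a respiratory-rate row to Table 6 with the sponsor's own low and high limits, applied to off-ventilator post-baseline values and counted by arm.
3. Flag ventilation status for AESI-triggered readings, so that readings taken on the ventilator stay out of both summaries. The extubation and re-ventilation dates and times recorded under Protocol 11.1.7 can supply the status.
4. State whether Table 6 is meant to cover temperature.

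The cost is SAP wording, a table footnote, one or two table rows and one entry in SAP 6.1. No new data are needed and no efficacy result changes. If the database is already locked, SAP 2 provides for documenting the change in the clinical study report.

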**Table 6: Potentially Clinically Significant Values for Vital Sign Parameters**

Vital Sign	Units	Criteria for PCS Values (Observed values)		Criteria for Change from Baseline values (PCSC)	
		High	Low	Increase	Decrease
Heart rate (supine and prone)	Beats/min	>120	<40	NA	NA
Systolic Blood Pressure (supine and prone)	mmHg	>180	<90	≥30	≥30
Diastolic Blood pressure (supine and prone)	mmHg	>110	<50	≥20	≥20

#### 8.4.5. Electrocardiogram

A 12-lead ECG will be performed at all scheduled time points. The standard intervals (heart rate, PR, QRS, QT, and QTcF) as well as any rhythm abnormalities will be recorded. Brief descriptive text should be included if the trace morphology is abnormal.

*Example:*

The observed value at each windowed visit and change from baseline at each post-baseline windowed visit will be summarized. Each ECG is evaluated by investigator as ‘normal’, ‘abnormal, not clinically significant’ and ‘abnormal, clinically significant’ in the eCRF; the number and percentage of participants with ‘abnormal, clinically significant’ or ‘abnormal, not clinically significant’ will be provided at baseline and each post-baseline windowed visit.

The number and percentage of participants with PCS and PCSC values will be summarized. PCS values will be identified for ECG parameters as outlined in [Table 7](#). In addition, the maximum value of QTcF if within any of the PCS criteria will be summarized.

**Table 7: Potentially Clinically Significant Values and Change for ECG Parameters**

ECG	Units	Criteria for PCS Values (Observed values)		Criteria for PCSC values (Change from Baseline)	
		High	Low	Increase	Decrease
QTcF Interval	msec	>450 but <=480 >480 but <=500 >500	NA	>=30 to 60 >60	NA

#### **8.4.6. Richmond Agitation Sedation Scale**

The RASS is a tool validated to assess sedation and agitation in ICU participants. RASS is a 10-point scale, with 4 levels of anxiety or agitation (+1 to +4 [combative]), one level to denote a calm and alert state (0), and 5 levels of sedation (-1 to -5) culminating in unarousable (-5).

The RASS will be administered once daily to all participants at the scheduled time points. In addition, the unscheduled RASS will be administered within 2 hours after each extubation. The unscheduled RASS will also be administered each time the decision is made to stop the IP infusion or reduce the dose.

Descriptive summaries of observed values will be provided for RASS- by windowed visit, and summarized by timepoint and treatment group. The unscheduled values will be presented in the listings.

#### **8.4.7. Confusion Assessment Method for the Intensive Care Unit**

The CAM-ICU score is a validated score to assess delirium in mechanically ventilated participants using standardized nonverbal assessments. The overall score is either “CAM-ICU Positive” or “CAM-ICU Negative”. The CAM-ICU will be administered every time RASS is assessed if RASS score  $\geq -3$ .

The listings of the observed values will be provided for CAM-ICU.

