### 7.4.2. Safety Criteria for Adjustment or Stopping Doses

Enrollment in the study will be discontinued if the DMC determines that any of the following criteria have been met:

1. there is an increased risk of mortality due to brexanolone
2. there is an increased risk of ICU delirium due to brexanolone
3. there is an increased risk of prolonged intubation due to brexanolone
4. there is an increased risk of reintubation due to brexanolone

After each data review, the DMC may recommend that the study continue without modifications, continue with modifications, or be terminated, or that study treatment or enrollment is suspended. The DMC may also recommend stopping the study for futility at the time of interim analysis.

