**12.1.8. Confusion Assessment Method for the Intensive Care Unit**

The CAM-ICU score is a validated score to assess delirium in mechanically ventilated patients using standardized nonverbal assessments ([Ely 2001](#)).

The CAM-ICU will be administered every time RASS is assessed if RASS score  $\geq$ -3.

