**Table 2: Visit Windows**

Scheduled Visit	Assessment Window	Analysis Visit Window	Study Day
V2	0 to 12h	>0 to $\leq$ 12h	1
V3	12h to 24h	>12h to $\leq$ 24h	1
V4	24h to 36h	>24h to $\leq$ 36h	2
V5	36h to 48h	>36h to $\leq$ 48h	2
V6	48h to 60h	>48h to $\leq$ 60h	3
V7	60h to 72h	>60h to $\leq$ 72h	3
Day 5 (V8)	Day 5	>72h to Day 5	3-5
Day 7 (V9)	Day 7	$\geq$ Day 6 to Day 10	6-10
Day 14 (V10)	Day 14	$\geq$ Day 11 to Day 17	11-17
Day 28 (V11)	Day 28	$\geq$ Day 25 to Day 31	25-31

Because endpoints are collected with different assessment schedules, some endpoint specific rules will be used:

- The clinical status assessed by RASS, and CAM-ICU in situations where RASS indicates appropriate subject alertness, will be administered daily and therefore will be windowed daily, from Day 1 through the end of study per-participant. If there is more than one assessment time point within the same day, the later assessment(s) will be used in the analysis.
- Hematology/Chemistry will be windowed according to the scheduled visits in the Protocol (Figure 1, page 11 – Visits 2 through 11). If there is more than one assessment within the scheduled visit, the later assessment will be used in the analysis.
- Vital signs will be windowed using the 12-hour interval as presented in [Table 2](#) above, up to Hour 72 (i.e., Visits 2 through 7). Starting from Day 5, it will be windowed daily, with the exception that Day 5 will be windowed as 72 hours –

Day 5. If there is more than one assessment within the same windowed time interval, the later assessment will be used in the analysis.

- Coagulation data is collected at Screening (Baseline), Visit 6, and Visit 9. Visit 6 will be windowed as 42 hours to 72 hours, and Visit 9 will windowed as 72 hours to Day 10.  
[REDACTED]  
[REDACTED]
- ECG is collected at Screening (Baseline), Visit 6, and Visit 10. Visit 6 will be windowed as 42 hours to 72 hours, and Visit 10 will windowed as Day 11 to Day 17.  
[REDACTED]

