## 8.4. Safety Analysis

Safety and tolerability of brexanolone will be evaluated by adverse events, concomitant medication usage, changes from baseline in vital signs, [REDACTED], clinical laboratory evaluations, RASS, CAM-ICU, and 12-lead ECG. Safety data, including adverse events of special interest (AESI), will be listed by participant and summarized by treatment group. All safety summaries will be performed on the Safety Analysis Set using actual treatment received. Assessments will be mapped to windows, with the choice of the record following the same rule as described in Section 8.1.2.

The safety endpoints and variables considered in the summary tables for this study are summarized in [Table 3](#).

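### CAM-ICU is named and windowed as a safety evaluation, but SAP 8.4.7 plans listings only, so no by-arm summary of the structured delirium measure is visible

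*SAP*

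**What the plan says.** SAP 8.4 (Safety Analysis) gives the evaluations on which safety will be judged, among them "clinical laboratory evaluations, RASS, CAM-ICU, and 12-lead ECG". The general rule follows: "Safety data, including adverse events of special interest (AESI), will be listed by participant and summarized by treatment group".

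SAP 8.1.2 (Visit Windows, in the rules after Table 2) treats RASS and CAM-ICU together. They "will be administered daily and therefore will be windowed daily", and where a day holds more than one assessment the later one goes into the analysis.

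The two instrument sections then differ:

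- SAP 8.4.6 on RASS: "Descriptive summaries of observed values will be provided for RASS- by windowed visit, and summarized by timepoint and treatment group".
- SAP 8.4.7 on CAM-ICU: "The listings of the observed values will be provided for CAM-ICU".

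Protocol 12.1.8 makes the assessment conditional: "The CAM-ICU will be administered every time RASS is assessed if RASS score" is −3 or higher. Protocol 7.4.2 includes among the four grounds on which the DMC would end enrolment that "there is an increased risk of ICU delirium due to brexanolone". Protocol 12.2.3 makes delirium an AESI.

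**The concern.** The general safety section promises a listing and a by-arm summary. The section for this instrument delivers only the listing. The daily windowing rule has no visible CAM-ICU analysis to serve.

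The gap falls on a safety question that the trial itself singles out. Delirium is both an AESI and a named DMC criterion, and CAM-ICU is the only structured delirium instrument in the visible documents. Without a table, the final report can compare delirium between arms only through events that an investigator chose to report. Anyone who wants the instrument's own result by arm must count it from the listings.

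A second issue bears on how such a table should be built. Protocol 7.4 says that brexanolone may potentiate co-administered sedatives, and a participant with RASS below −3 has no CAM-ICU. The share of assessments at which delirium can be detected may therefore differ between arms.

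**Working it through.** The plan states no figure for CAM-ICU, so there is none to reproduce. The check is mainly one of text against text.

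**1. What each safety measure receives**

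| Measure | Named in SAP 8.4 | Windowed in 8.1.2 | Planned output |
|---|---|---|---|
| RASS | yes | daily | summary by timepoint and treatment group (8.4.6) |
| CAM-ICU | yes | daily | listing only (8.4.7) |
| Delirium AESI | yes, as AESI | not applicable | separate AESI tabulation (8.4.1) |

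SAP Table 3 has no CAM-ICU row. That is not decisive, because it has no RASS row either and RASS is summarized.

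**2. Was the summary dropped on purpose?** The visible part of SAP 6.1 records changes from the protocol, including analyses dropped at early termination: the odds ratio, Kaplan-Meier, tipping-point and interim analyses and the Per-Protocol set. CAM-ICU is not among them, and no reason for listing only is given. Visible Protocol 13.6 does not name CAM-ICU, so the conflict is internal to the SAP.

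**3. Does the AESI table stand in for it?** SAP 8.4.1 finds AESIs by screening coded adverse-event terms and querying the hits. Protocol 12.2.1 says when laboratory, vital-sign and ECG changes count as adverse events. No visible rule says when a positive CAM-ICU does. A positive assessment may be reported as an AESI, but need not be.

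**4. Why the denominator matters.** In one arm, let *a* be the share of scheduled assessments with RASS −3 or higher, and *d* the share positive among those.

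- Positives per scheduled assessment = *a* × *d*.
- If *d* is equal in both arms, the ratio of positive counts, brexanolone to placebo, is *a*(brexanolone) / *a*(placebo). It differs from 1 whenever assessability differs.
- Positives divided by assessable assessments = *d*, which removes that artefact.

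The documents give neither *a* nor *d*. Dividing by assessable assessments also conditions on a state reached after randomization. The ratio is therefore descriptive and should stand beside the count not assessable.

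**5. How precise could a by-arm figure be?** Assume the same true ever-positive rate *p* in both arms and *n* per arm. The 95% half-width for the difference is 1.96 × √(2*p*(1−*p*)/*n*). For *p* = 0.20 and *n* = 50 this is 1.96 × √(0.32/50) = 0.157.

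| *n* per arm | *p* = 20% | *p* = 40% or 60% |
|---|---|---|
| 50 (planned) | 15.7 points | 19.2 points |
| 25 (assumed) | 22.2 points | 27.2 points |
| 10 (assumed) | 35.1 points | 42.9 points |

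The rates are assumptions, and so are the two smaller sample sizes, because enrolment at termination is not stated. The widths argue for description without testing.

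**The case against.** The case against runs as follows. Delirium is already captured prospectively: it is a predefined AESI, sent on its own form within 72 hours with detail on orientation after extubation, screened by term, queried and tabulated separately. RASS by arm shows sedation depth, and the listings keep every CAM-ICU result. The trial was already ending for recruitment reasons, so a wide descriptive estimate adds little. Parts of the SAP are redacted and the list of displays (Appendix B) is not shown, so a CAM-ICU table may exist.

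Much of this stands. It makes the point minor and confines it to the visible text. It does not remove the conflict between 8.4 and 8.4.7. RASS summaries also do not give positives over assessable assessments.

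Three stronger readings are tempting and are not supported:

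- *Delirium is left to spontaneous reports.* Protocol 12.2.5 also covers observed events and open questions, and the AESI process is structured.
- *The DMC could not judge its delirium criterion.* The SAP governs the final analysis. Under the protocol the DMC receives AESIs on an ongoing basis and has unblinded safety data at meetings held at least monthly. Its charter is not among the documents, and 8.4.7 does not show what it saw.
- *The trial will show a false delirium benefit caused by sedation.* The SAP plans no count that could mislead in this way. The infusion lasts 60 hours, Protocol 5.1 describes the drug as rapidly cleared, and Protocol 7.4 has co-administered sedatives titrated to the desired effect. A large, lasting gap in assessability would be an assumption.

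**Conclusion.** The point holds as an internal inconsistency of minor severity. SAP 8.4 and 8.1.2 lead the reader to expect CAM-ICU by arm, and 8.4.7 provides only a listing. In the visible final analysis, the comparison of delirium between arms rests on investigator-reported AE and AESI data.

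The gap covers every CAM-ICU result. No numerical bias can be attached to it, because the documents give no CAM-ICU rates, no share assessable and no enrolled number. The primary and key secondary analyses are untouched. The conclusion assumes that no CAM-ICU summary sits in the redacted sections or in the list of displays.

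**What to change.** Replace the sentence in SAP 8.4.7 with a descriptive table on the Safety Set by actual treatment, without hypothesis tests, and keep the listing. Present it for the infusion period and, separately, for the later in-hospital period through Day 28. Give:

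- number and percent of participants ever CAM-ICU positive;
- positive assessments over assessable assessments (RASS −3 or higher);
- among participants alive and in hospital, scheduled assessments not assessable because RASS was below −3;
- separate counts for death, discharge and missed assessments. After discharge only assessments that can be done by phone continue, so pooling these with deep sedation would make the count uninterpretable.

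State whether the ever-positive count uses all assessments or only the one kept per day under 8.1.2.

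If listing only is intended, amend 8.4 to say so and give the reason. That settles the inconsistency but leaves the instrument unreported by arm.

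The cost is one table from data already collected and windowed: a free improvement. If the database is already locked, SAP section 2 provides for documenting the change in the clinical study report.
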